10.0 Statistical Considerations

10.1. Sample size justification :

In this pilot protocol, it is anticipated that 37 patients will be enrolled to receive boost therapy. This number of patients will provide a 10% level of precision (half-width of a 90% confidence interval) for the true (unknown) proportion of subjects that will experience toxicity-limiting pneumonitis. The investigators believe this proportion will be no greater than 20% and have used this number in the sample size justification based on the 90% confidence interval width.

10.2 Stopping rules for severe pneumonitis:

We anticipate that pneumonitis may be the most common radiation-related side effect, and patients will be closely monitored for development of severe pneumonitis in this study. An historical rate of severe pneumonitis rate has been documented to be as high as 15% but varies depending on the volume of lung being irradiated (12). Treatment of most stage III lung cancers carry risks in the 15% and higher range due to volumes of lung irradiated. As such, the protocol will be stopped if sufficient evidence exists suggesting that, among patients receiving therapy, the true incidence of severe pneumonitis exceeds 15%. Sufficient evidence will be statistically defined in the form of an estimate for the severe pneumonitis rate (binomial proportion) whose lower 90% confidence limit exceeds 15%, and these estimates will be made after every 5th enrolled patient to the study. Operationally, any of the following observed ratios (# experiencing severe

pneumonitis of total number observed) would lead to exceeding such a limit: 3 or more of the first 5; 4 or more of the first 10; 5 or more of the first 15; and 6 or more of the first 20.

If the true probability of severe pneumonitis incidence is 10%, the probability of stopping the study under these rules is less than 1% after enrollment of 5 patients on the study, <1.3% after enrollment of the first 10, and roughly <1% after enrollment of 20 patients on the study. If the true probability is 20%, then the probability of stopping after 5, 10, and 20 patients is 6%, 12% and 19%, respectively. If the true probability is 40%, the probability of stopping after 5, 10, and 20 patients is approximately 32%, 62%, and 88%, respectively.

11. Reporting Toxicity

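### Section 10.2 checks the severe-pneumonitis limits only at every fifth enrolment, so a few patients could be boosted after the formal stop is already certain

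*Combined protocol and SAP*

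**What the plan says.** Section 10.2 stops the protocol when the evidence suggests a true severe-pneumonitis incidence above 15%. Evidence is sufficient when the estimated proportion is one "whose lower 90% confidence limit exceeds 15" per cent. On timing, "these estimates will be made after every 5th enrolled patient to the study". The operating limits are "3 or more of the first 5; 4 or more of the first 10; 5 or more of the first 15", and finally "6 or more of the first 20". The section does not say what happens if a count reaches a limit before the look to which it belongs.

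Other sections bear on this:
- Section 9.0 makes the principal investigator primarily responsible for safety monitoring. It also allows several committees and the IRB to suspend accrual at once for patient-safety reasons.
- Section 11 requires radiation-attributable grade 4 and 5 toxicities to be reported to the DSMB and IRB within 24 hours.
- Sections 8.2.1 and 11 follow toxicity for 6 months after the boost.
- Section 2.0 makes estimation of the pneumonitis proportion the primary objective.

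**The concern.** A cumulative case count never goes down. If 4 severe cases have occurred among the first 7 patients, the limit of 4 among the first 10 will be met whatever happens to patients 8, 9 and 10. A rule that is evaluated only when patient 10 has been enrolled leaves room to boost those three patients after its own result is settled. Their outcomes cannot change the decision. At stake is the exposure of a small number of patients to a boost that the plan's own criterion would by then have judged too toxic.

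**Working it through.** **Inputs.** From section 10.2: limits of 3/5, 4/10, 5/15 and 6/20, with looks at n = 5, 10, 15 and 20. From section 10.1: "it is anticipated that 37 patients will be enrolled to receive boost therapy", used as the number treated when the rule never stops the trial. The Schema says 42, but the choice does not affect the saving, because a trial that is not stopped saves no one. Assumption: each outcome is known before the next patient is treated.

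**1. The plan's own figures.** With X ~ Binomial(n, p), the tail P(X ≥ r) at each look taken alone gives:

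| True rate | n = 5 | n = 10 | n = 20 | Plan states |
|---|---|---|---|---|
| 10% | 0.86% | 1.28% | 1.13% | "less than 1% after enrollment of 5 patients on the study, <1.3% after enrollment of the first 10, and roughly <1% after enrollment of 20" |
| 20% | 5.8% | 12.1% | 19.6% | "the probability of stopping after 5, 10, and 20 patients is 6%, 12% and 19%, respectively" |
| 40% | 31.7% | 61.8% | 87.4% | "the probability of stopping after 5, 10, and 20 patients is approximately 32%, 62%, and 88%, respectively" |

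For example, at p = 0.20 and n = 5: 10(0.2³)(0.8²) + 5(0.2⁴)(0.8) + 0.2⁵ = 0.0512 + 0.0064 + 0.0003 = 0.0579. The stated figures are therefore single-look probabilities and reproduce closely; 1.13% lies slightly above the stated bound. The figures below are cumulative over the looks, which is why they are higher.

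**2. The evidence criterion.** The exact one-sided 90% lower limits at 3/5, 4/10, 5/15 and 6/20 are 24.7%, 18.8%, 17.2% and 16.6%, all above 15%. One case fewer gives 11.2%, 11.6%, 12.2% and 12.7%, all below. Reaching a limit early is stronger evidence still: 4/7 gives 27.9%, 5/12 gives 21.9% and 6/17 gives 19.7%.

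**3. How early a stop can be certain.** Before the first look, 3 cases in 3 patients settle it, so 5 − 3 = 2 patients remain. After a look that did not stop the trial, the count is at most 2, 3 or 4, and the next limit is 4, 5 or 6, so at least two more cases are needed. The earliest settled points are patients 7, 12 and 17, which leaves 10 − 7 = 15 − 12 = 20 − 17 = 3 patients.

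**4. Stopping probability with and without waiting.** A count reaches its limit at or before patient n exactly when the count at patient n is at or above the limit. The two rules therefore stop the same trials. An exact patient-by-patient recursion confirms this. At a true 20%, both give 5.8%, 13.8%, 20.6% and 26.1% by patients 5, 10, 15 and 20.

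**5. Patients spared.** E(N) is the expected number treated.

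| True rate | P(stop by 20), both rules | E(N) waiting | E(N) acting at once | Saving, all trials | Saving per stopped trial | Certain early, among stops |
|---|---|---|---|---|---|---|
| 10% | 2.8% | 36.28 | 36.26 | 0.02 | 0.8 | 53% |
| 15% | 11.0% | 34.25 | 34.15 | 0.10 | 0.9 | 56% |
| 20% | 26.1% | 30.56 | 30.31 | 0.25 | 0.9 | 58% |
| 30% | 64.3% | 20.73 | 20.06 | 0.68 | 1.1 | 63% |
| 40% | 89.8% | 12.93 | 11.91 | 1.02 | 1.1 | 67% |

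Savings were computed before rounding. The saving per stopped trial is the saving over all trials divided by P(stop); at 20%, 0.246 / 0.2611 = 0.94.

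**6. Effect on the estimate.** At a true 20%, the mean raw proportion (cases divided by patients treated, over all trials) is 24.3% with waiting and 25.1% when acting at once. The root mean squared error is 0.140 and 0.162 respectively.

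**The case against.** The strongest reply is that section 10.2 schedules the estimates but does not forbid earlier action. Four cases among seven patients arguably already satisfy the limit for the first ten, nothing tells investigators to keep enrolling, and the section promises close monitoring. Sections 9.0 and 11 add routes to immediate suspension and rapid reporting. A reader might infer that patients will inevitably be boosted after the stop is certain; the documents do not support that. What stands is narrower. The powers in section 9.0 are discretionary, the 24-hour report covers only attributable grade 4 and 5 events, and neither is tied to the count in 10.2. A prespecified rule should not need discretion to act on its own settled result.

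A reader might also infer that waiting has no statistical value at all. That holds for the stopping decision only. The primary objective is to estimate the pneumonitis proportion, and step 6 shows that waiting gives a slightly less biased and less variable raw estimate.

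The effect is also small, and figures per stopped trial make it look larger than it is. At true rates up to the 20% that section 10.1 treats as the ceiling for toxicity-limiting pneumonitis, the average saving over all trials is at most 0.25 patients. Finally, immediate outcomes are doubtful when toxicity is followed for 6 months. Both objections stand. They limit the size of the point but leave its logic intact: whenever the observed count reaches a listed limit, any patient not yet boosted can be spared.

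**Conclusion.** The point holds as a low-cost refinement of the formal rule. It is not an error in the limits or a failure of safety oversight. Read as written, section 10.2 allows up to 3 further patients to be boosted after the stop is certain, and acting at once changes no stopping probability. The expected gain is about one patient per stopped trial, and between 0.02 and 1.02 patients over all trials at true rates of 10% to 40%.

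These sizes, and the maximum of 3, assume that each outcome is known before the next patient is treated. They cover only the looks to patient 20, because no limits are listed beyond it. With delayed onset the saving depends on accrual speed and on when pneumonitis appears within the 6-month window. The documents give neither, so the realised figure could differ.

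**What to change.** Add one sentence to section 10.2: *A listed limit is met, and accrual stops, as soon as the number of severe pneumonitis cases observed among the first 5, 10, 15 or 20 patients reaches that limit, whether or not the whole cohort has been enrolled or a scheduled look is due.*

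The wording is tied to the named cohorts on purpose. A trigger tied to the next scheduled look would miss a fourth case among the first 10 that comes to light after patient 11 is enrolled, because the next look's limit is then 5. The sentence above covers both situations.

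The limits stay as they are, and with immediate outcomes so do the stopping probabilities. If outcomes are delayed, the sentence also counts late cases in a cohort whose look has passed, which a once-only look would not. The costs are that the running count must be checked at each new case, and that the raw estimate is slightly worse when the trial stops early, as shown in the working.

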07-RAD-01-UK/P4:
Stereotactic Body Radiation Therapy for Post-chemoradiation
Residual Disease in Stage II/III Non-small Cell Lung Cancer

Principle Investigator:

[name]., Ph.D.
Department of Radiation Medicine
University of Kentucky

Medical Oncology Co-Investigators:

[name].
[name].
Department of Hematology/Oncology,
University of Kentucky

Imaging Co-Investigators:

[name].
[name].
Department of Diagnostic Radiology,
University of Kentucky

Statistical Co-Investigator:

[figure not shown]
[name].
Departments of Internal Medicine & Biostatistics
University of Kentucky Colleges of Medicine & Public Health

Study version 1.5.2 July 8, 2013

SCHEMA

Eligible patients with Stage II/III NSCLC[#]

Completed Definitive Chemoradiation to min 5940 cGy*

[figure not shown]

CT scan or PET/CT 21-30 days post chemo RT

SBRT boost

Peripheral Tumors: 1000cGy X 2 to residual primary mass

Medial Tumors: 650cGy x 3 to residual primary mass

Routine Followup with CT chest and/or chest x-ray at ~3 months

PET/CT if suspected recurrence/metastasis clinically indicated

Sample size: 42 patients

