8.2 Baseline documentation of Target and Non-target lesions

The longest diameter (LD) for the target lesion will be calculated from the treatment planning CT scan using pulmonary windowing and reported as the baseline LD. The baseline LD will be used as the reference by which to characterize the objective tumor response. For follow-up assessment, diagnostic CT scans using lung windows are the preferred modality. Local treatment effects in the vicinity of the tumor target may make determination of tumor dimensions difficult e.g. patchy consolidation.

All other lesions which appear or enlarge after treatment e.g. regional lymph nodes and distant metastases should be identified as non-target lesions and should be recorded at the time of their appearance/suspicious enlargement. Patients who have suspicious CT scans may have PET/CT to assess local failure/distant metastasis as per clinical judgment.

8.2.1. Post treatment followup - Followup evaluation will be performed approximately 30 days after completion of all protocol treatment to assess toxicity and tumor response.

Follow-up for evaluation of toxicity will continue for 6 months following SBRT delivery. Additional follow-up for local control and survival will continue until death or study withdrawal.

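### Section 10.2's stopping probabilities ignore earlier looks, so the 10- and 20-patient figures are too low, and nothing is listed for looks after patient 20

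*Combined protocol and SAP*

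**What the plan says.** Section 10.2 stops the protocol on sufficient evidence that "the true incidence of severe pneumonitis exceeds 15"%. The evidence required is an estimated binomial proportion "whose lower 90% confidence limit exceeds 15"%, and "these estimates will be made after every 5th enrolled patient to the study". Four limits are listed, and reaching any one of them is enough to stop: 3 of 5, 4 of 10, "5 or more of the first 15; and 6 or more of the first 20".

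The next paragraph gives the chance of stopping under these rules after 5, 10 and 20 patients:

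- True rate 10%: below 1% at 5 patients, then "<1.3% after enrollment of the first 10, and roughly <1% after enrollment of 20 patients on the study".
- True rate 20%: "If the true probability is 20%, then the probability of stopping after 5, 10, and 20 patients is 6%, 12% and 19%, respectively".
- True rate 40%: about 32%, 62% and 88%.

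Planned enrolment is 37 in Section 10.1, while the Schema has "Sample size: 42 patients". On toxicity follow-up, Section 8.2.1 says: "Follow-up for evaluation of toxicity will continue for 6 months following SBRT delivery".

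**The concern.** Because a crossing at any look ends the trial, the chance of having stopped by patient 20 includes crossings at 5, 10 and 15. It can only rise or stay level as looks are added. The printed 10% row goes down between 10 and 20 patients, so the text alone shows that these are not probabilities of having stopped.

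These sentences are the only stated operating characteristics of the trial's only numeric stopping rule. Whoever approves or oversees the trial would use them to judge how often it stops when the true rate is acceptable and how reliably it stops when the rate is high. Three things that such a reader needs are missing:

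- a probability at 15%, the rate on which the rule turns;
- limits and probabilities for the looks after patient 20, which the every-fifth-patient rule requires at 25, 30 and 35 (and at 40 if 42 are enrolled);
- the interval method and whether the 90% limit is one-sided or two-sided.

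**Working it through.** **Inputs (Section 10.2).** Looks at n = 5, 10, 15, 20; limits r = 3, 4, 5, 6; true rates p = 10%, 20%, 40%; threshold 15%.

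**1. Reproduce the printed figures.** Treat each look as the only one: P(X ≥ r), with X ~ Binomial(n, p).

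| True rate | n = 5: printed / single look | n = 10: printed / single look | n = 20: printed / single look |
|---|---|---|---|
| 10% | <1% / 0.86% | <1.3% / 1.28% | roughly <1% / 1.13% |
| 20% | 6% / 5.8% | 12% / 12.1% | 19% / 19.6% |
| 40% | 32% / 31.7% | 62% / 61.8% | 88% / 87.4% |

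All nine agree within loose rounding. Reading the figures as the chance of stopping for the first time at that look does not fit: at 20% that gives 5.8%, 8.0% and 5.6%, against the printed 6%, 12% and 19%.

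**2. Accumulate over looks.** At each look, take the distribution of the event count among trials that have not stopped, add five patients, count the share at or above the limit as newly stopped, and carry the rest forward. At p = 0.20:

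- Look 5: P(X ≥ 3) = 0.0579. The continuing paths have 0, 1 or 2 events, with probabilities 0.3277, 0.4096 and 0.2048.
- Look 10 (limit 4): these paths need at least 4, 3 or 2 events in the next five patients, with probabilities 0.0067, 0.0579 and 0.2627. New stops = 0.3277 × 0.0067 + 0.4096 × 0.0579 + 0.2048 × 0.2627 = 0.0797.
- Looks 15 and 20, in the same way: 0.0678 and 0.0557.
- Total by 20: 0.0579 + 0.0797 + 0.0678 + 0.0557 = 0.2611.

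Cumulative probability of having stopped:

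| True rate | by 5 | by 10 | by 15 | by 20 |
|---|---|---|---|---|
| 10% | 0.9% | 1.8% | 2.4% | 2.8% |
| 15% | 2.7% | 6.1% | 8.9% | 11.0% |
| 20% | 5.8% | 13.8% | 20.6% | 26.1% |
| 40% | 31.7% | 63.6% | 80.8% | 89.8% |

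Simulation (400,000 trials at each of 10%, 20% and 40%) gives 2.8%, 26.2% and 89.8% by patient 20.

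**3. Which interval gives the listed limits?** The one-sided 90% exact lower limit is the 0.10 quantile of Beta(r, n − r + 1).

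| r/n | 3/5 | 4/10 | 5/15 | 6/20 | 7/25 | 8/30 | 9/35 | 10/40 |
|---|---|---|---|---|---|---|---|---|
| Lower limit | 0.247 | 0.188 | 0.172 | 0.166 | 0.163 | 0.162 | 0.162 | 0.162 |

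One event fewer puts the limit below 0.15 at every look (0.112 to 0.141). This interval therefore reproduces all four listed limits and implies 7/25, 8/30, 9/35 and 10/40. The lower end of a two-sided 90% exact interval is 0.142 at 5/15 and 0.140 at 6/20. It would need 6/15 and 7/20, so it is not the interval behind the list.

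**4. Continue with those later limits.**

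| True rate | stopped by 35 | stopped by 40 |
|---|---|---|
| 10% | 3.3% | 3.4% |
| 15% | 15.3% | 16.2% |
| 20% | 37.9% | 40.8% |
| 40% | 98.3% | 99.1% |

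**5. Outcomes not yet known at a look.** Toxicity is followed for 6 months, and the plan gives no accrual rate. As an assumed illustration, let the 5 most recently enrolled patients not yet be evaluable. Stopping by 20 enrolled then equals the 15-patient column in step 2: 2.4%, 8.9%, 20.6% and 80.8% at 10%, 15%, 20% and 40%.

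**The case against.** The strongest case against concerns weight rather than arithmetic.

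- **Most gaps are small.** Of the six figures at 10 and 20 patients, five differ from the cumulative value by less than 2 percentage points. Only 20% at patient 20 differs by much (about 7 points). The broad message survives: stopping is rare at 10% and close to 90% by patient 20 at 40%. This stands, although at 10% the cumulative 1.8% and 2.8% both break the printed upper bounds.
- **Patients are not less protected.** No listed limit changes, the rule stops more readily than stated, and under Section 9.0 the oversight bodies may suspend accrual on safety grounds without any numeric rule. This also stands. The defect is in how the rule is described.
- **The direction depends on evaluability.** With the assumed 5-patient lag, the chance by 20 enrolled at a true 40% is 80.8%, below the printed 88%. This is fair, and the assumption should be stated. It does not rescue the printed figures, because the single-look tails that they match also count every patient's outcome. At a true 10%, even the lagged 2.4% exceeds the printed value.
- **Later looks are covered by the general rule.** Monitoring is indeed not missing after patient 20. The one-sided exact, one-sided Wald, two-sided 90% Wilson and two-sided 90% Jeffreys limits all reproduce the listed limits and all give 7/25, 8/30, 9/35 and 10/40. But a reader must work back from the list to find this. Someone who applies a two-sided exact interval would arrive at 8/25, 9/30, 10/35 and 11/40.
- **A 15% row is optional.** Nothing in the plan promises one. Its absence is an omission rather than a miscalculation, but it is the most informative row for a rule built on 15%.

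**Conclusion.** The concern holds and should be fixed. The 5-patient probabilities are correct, since there is no earlier look. The 10- and 20-patient values were calculated as if each look stood alone, and they understate the chance of stopping. The largest absolute gap is 26.1% against 19% (true 20%, patient 20). The largest relative gap is 2.8% against roughly below 1% (true 10%, patient 20). At exactly 15%, where a stop would be a false alarm, the undisclosed chance is 11.0% by patient 20 and 15.3% by patient 35.

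The values up to patient 20 rest on the listed limits, independent patients with a common rate, and outcomes known at each look. Those after patient 20 also assume the limits 7/25, 8/30 and 9/35. If outcomes lag enrolment, stopping by a given enrolment is less likely.

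**What to change.** In Section 10.2:

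1. Replace the probabilities with cumulative values at 5, 10 and 20 patients: 0.9%, 1.8%, 2.8% at a true 10%; 2.7%, 6.1%, 11.0% at 15%; 5.8%, 13.8%, 26.1% at 20%; 31.7%, 63.6%, 89.8% at 40%.
2. State that they assume each patient's outcome is known at the look, and that with 6 months of toxicity follow-up the chance of stopping by a given enrolment could be lower.
3. Name the interval and its sidedness. A one-sided 90% exact limit agrees with all four listed limits.
4. List the limits that the named interval implies for the remaining looks (for the one-sided exact limit, 7/25, 8/30, 9/35 and, if 42 are enrolled, 10/40), with cumulative probabilities through the last look. The last look depends on whether 37 or 42 patients are planned, so Section 10.1 and the Schema must be reconciled first.

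The cost is protocol wording. No listed limit or look changes. The one drawback is that the stated chance of a false stop at true rates of 15% or below looks somewhat less favourable.
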